6. RECRUITMENT METHODS

- *Describe the source of potential subjects*
- *Describe the methods that will be used to identify potential subjects*
- *Describe any materials that will be used to recruit subjects. A copy of any advertisements (flyers, radio scripts, etc.) should be submitted along with the protocol.*
- *If monetary compensation is to be offered, this should be indicated in the protocol*

Eligible care partners will be identified via 3 steps:

- 1) Using a previously developed EHR identification tool described in Section 5, a data analyst from QI will generate a list of potentially-eligible patients
- 2) a consenting coordinator will conduct a chart review of the QI-generated list to confirm eligibility described in Section 7, and
- 3) the consenting coordinator will call the care partner while the patient is still hospitalized, introduce the study, confirm patient and care partner eligibility, confirm that the patient is being discharged home, and offer study participation.

For care partners who are considered screen failures, the consenting coordinator will record demographic information, including the NIA-required Clinical Research Operations & Management System (CROMS) screen failure questionnaire (see Section 14).

A flyer with more information about the study will be given to potential participants that may be interested in consenting at a later time.

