8. NUMBER OF SUBJECTS

- *Indicate the total number of subjects to be accrued locally. If applicable, distinguish between the number of subjects who are expected to be pre-screened, enrolled (consent obtained), randomized and complete the research procedures.*
- *If your study includes different cohorts, include the total number of subjects in each cohort.*
- *If this is multisite study, include total number of subjects across all sites.*

The study expects to screen up to 350 potential care partners for eligibility to enroll N=80 care partners into the study. Of the N=80 participants enrolled, N=40 will be randomized (blind allocation) to an enhanced control condition (usual care, with speech language pathologist [SLP] contact information) and the remaining N=40 will be randomized to the intervention condition (usual care, with SLP contact information + WeCareToFeedDysphagia). We anticipate at least N=60 (25% attrition) participants will complete research procedures.

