11. RESEARCH PROCEDURES

- *Include a detailed description of all procedures to be performed on the research subject and the schedule for each procedure.*
- *Include any screening procedures for eligibility and/or baseline diagnostic tests*
- *Include procedures being performed to monitor subjects for safety or minimize risks*
- *Include information about drug washout periods*
- *If drugs or biologics are being administered provide information on dosing and route of administration*
- *Clearly indicate which procedures are only being conducted for research purposes.*
- *If any specimens will be used for this research, explain whether they are being collected specifically for research purposes.*
- *Describe any source records that will be used to collect data about subjects*
- *Indicate the data to be collected, including long term follow-up*

[figure not shown]
We will identify potentially eligible care partners by pre-screening the EHR and conducting a chart review. Using a previously developed EHR identification tool described in Section 5, a data analyst will generate a list of potentially-eligible patients and provide a link to the data file via a PHI-secured SharePoint site. A consenting coordinator will review these patient records to confirm potential eligibility using the inclusion and exclusion criteria described in Section 7. The consenting coordinator will contact the care partner, offer a study description, confirm interest in participation, evaluate care partner and patient eligibility, review the verbal HIPAA authorization and consent information and collect verbal consent from the care partner (for themselves and surrogate consent on behalf of the individual for whom they provide care). The consenting coordinator will then send the participant via text-message a link to a REDCap survey to document consent and authorization, and complete the Time Point 1 (baseline) measures. If the care partner prefers, Time Point 1 will occur virtually with the care partner using Microsoft Teams or Zoom. The consenting coordinator will reiterate the purpose of the research and answer any questions.

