We will randomize (blind allocation) the care partner to either the enhanced condition (usual care, including speech language pathologist (SLP) contact information) or the intervention (usual care, including SLP contact information, + WeCareToFeedDysphagia). The study team will collect in the Time Point 1 measures, sociodemographic information, caregiving measures, as well as baseline

ZBI-22, CarerQol, CARES Part A and Part B, EdFED-Q, and QUALID via REDCap. In addition, the study team will collect relevant clinical data from the patient record (see Section 14 for a full list of variables collected via EHR and care partner survey).

Enhanced Control Condition (n=40)

In the enhanced control condition, following completion of baseline measures, the care partner will continue to receive usual care from the patient's medical team. The study team will provide information regarding contacting a speech language pathologist for further information regarding caring for someone with AD/ABRD and OD. The care partners will also receive information regarding contact for remaining study assessments (1 month and 3 months post-discharge).

Intervention Condition (N=40)

In the intervention condition, following completion of baseline measures, the care partner will continue to receive usual care from the patient's medical team, plus the study team will provide access to WeCareToFeedDysphagia. The study team will provide all participants a copy of the information sheet, the team's contact information, and a reminder that study personnel will contact them by phone 1 week post-discharge to assess tool use and answer any questions. The study team will provide unique

usernames and passwords to participants in the intervention condition and instructions on how to access WeCareToFeedDysphagia from any smart device (e.g., smartphone) or computer. Care partners will receive a text message reminder about the WeCareToFeedDysphagia resource 1 week, 2 weeks, and 3 weeks after initial access is granted to the care giver.

Participants in both the enhanced control condition and the intervention condition will receive text message link to complete repeat assessments of the ZBI-22, CarerQol, CARES Part A and Part B, EdFED-Q, and QUALID one month post-hospital discharge (Time Point 2) and 3 months post-hospital discharge (Time Point 3) via REDCap. For those care partners who are unable to complete the REDCap survey on their own, a member of the study team will set up a 30-minute

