continuous variables, and frequency and proportion for categorical variables. Our primary analysis will be to compute the ES between each pair of means on the measure of burden (our primary outcome) at the 3-month assessment. For example, we will compute the ES for Condition 1 versus Condition 2 as $(\text{Mean 1} - \text{Mean 2}) / \text{Standard Deviation}$. The ES will inform our sample size and power considerations for the future full-scale RCT.

Secondary Outcomes:

- Care partner burden at 1 month post-discharge
- Care-Related Quality of Life (CarerQoL) at 1 month and 3 months post-discharge
- Percent tool engagement (Go/No-Go)
- Percent consented (Go/No-Go)
- Percent attrition at 1 month and 3 months post-discharge (Go/No-Go)

Exploratory Outcomes:

- Mediating measures:
 - CARES Part A at 1 month and 3 months post-discharge (mediating measures)
 - CARES Part B at 1 month and 3 months post-discharge (mediating measures)
 - Sociodemographics
 - Clinical data
 - Caregiving measures
- EdFED-Q at 1 month and 3 months post-discharge
- QUALID at 1 month and 3 months post-discharge
- Patient-centered outcomes at 1-month and 3 months post-discharge

Sample Size Considerations

Because this study is designed to inform the sample size calculations for a future full-scale efficacy RCT, we plan to enroll 10% of the projected sample size needed for the full-scale RCT ($N=60$ or 10% of 602, see Figure 2 and power calculation). To account for an attrition rate of 25% (based on patient mortality and care partner loss to follow-up) at 3 months, a total of $N=80$ or $n=40$ in each condition (enhanced control and intervention) is needed for the pilot RCT (increase from $N=60$ to $N=80$ based on 60×1.33 -attrition calculation). To meet our 6-month recruitment goal of $N=80$, we will need to recruit ~4 care partners per week. Based on our preliminary work demonstrating an average of ~11 eligible care partners/week, we should have no issues reaching recruitment goals for this study.

Blind Allocation Procedures

Randomized allocation will be pre-generated via code and uploaded to a REDCap file accessible only to members of the Institute of Health System Science data team. The consenting coordinator will email a member of the data team for the next allocation prior to each individual consent.

--

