23. CONSENT PROCESS

If obtaining consent for this study, describe:

- *Who will be obtaining consent*
- *Where consent will be obtained*
- *Any waiting period available between informing the prospective participant and obtaining consent*
- *Steps that will be taken to assure the participants' understanding*
- *Any tools that will be utilized during the consent process*
- *Information about how the consent will be documented in writing. If using a standard consent form, indicate such.*
- *Procedures for maintaining informed consent.*

A consenting coordinator will pre-screen patient records for potential participants via hospital visit information, age, race, ethnicity, gender, sex, history of dementia, OD diagnosis, and legally authorized representative (LAR) or health care proxy (HCP). For those eligible, the consenting coordinator will contact the LAR or HCP (who might be the same person or who might direct the research team to another care partner) to provide study information and offer the opportunity to participate. The EMR will be reviewed for contact information to speak with the LAR/HCP via phone. The research team member will verbally offer the LAR/HCP or other care partner information about the study, explain all aspects of study participation, and state that participation of the study is voluntary, that the care partner may opt out at any time, and that the decision to decline to participate or to opt out will not affect the patient's treatment.

After verbal consent and authorization, the consenting coordinator will send a text-message with a link to REDCap hosted econsent to document their consent and authorization to participate. After the form's submission, the consenting coordinator who undertook the consent process will review the form for completion and use the REDCap Locking and E-signature functions on the form to disable future changes to the form. The E-signature function will require the consenting coordinator to enter their Northwell credentials to authenticate the signature. The participant will be considered enrolled once the consent form has been reviewed for an acceptable signature and the consenting coordinator has E-signed the form.

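### The recruiter requests the next allocation before consent, and nothing says the reply is held back, so allocation concealment is not secured

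*Combined protocol and SAP*

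**What the plan says.** Under Blind Allocation Procedures, Section 12 keeps the full list away from recruiters. It is "pre-generated via code and uploaded to a REDCap file accessible only to members of the Institute of Health System Science data team". The next sentence says how an assignment leaves that list: "The consenting coordinator will email a member of the data team for the next allocation prior to each individual consent".

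The person who sends that email controls entry to the trial. In Section 6, "the consenting coordinator will call the care partner while the patient is still hospitalized, introduce the study, confirm patient and care partner eligibility", and then offers participation. In Section 11 the coordinator must also "confirm interest in participation, evaluate care partner and patient eligibility", take verbal consent, and text the link to the e-consent and the Time Point 1 survey. Section 23 puts enrolment later still: "The participant will be considered enrolled once the consent form has been reviewed for an acceptable signature" and the coordinator has countersigned electronically.

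Two other sections imply the opposite order. Section 8 says: "Of the N=80 participants enrolled, N=40 will be randomized (blind allocation) to an enhanced control condition". Section 11, after describing consent and the baseline link, says: "We will randomize (blind allocation) the care partner to either the enhanced condition". Neither gives a mechanism.

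The primary analysis in Section 12 is the difference between the two 3-month burden means divided by a standard deviation. No baseline adjustment is stated. The result is meant to size the full-scale trial.

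**The concern.** Concealment needs two things: the recruiter cannot see the list, and the recruiter does not learn the next assignment until the participant is irrevocably in. The plan secures the first. On the second, its only operational sentence places the request before consent and is silent about the reply.

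Several entry criteria in Section 7 call for judgement over the phone, such as who counts as the primary care partner, whether that person will be involved in dysphagia management after discharge, and English proficiency. A coordinator who knows the next arm could, without intending to, apply these criteria differently or present the study differently according to the arm. Any resulting difference in prognosis between arms would pass into the unadjusted effect size. A larger trial reduces random error but does not remove selection bias, and analysis cannot fully restore lost concealment.

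**Working it through.** **1. The plan's own sample size.** Section 12 takes 10% of 602, which is 60.2, stated as 60 completers. Allowing for 25% attrition, 60 / (1 - 0.25) = 80; the plan's shortcut is 60 x 1.33 = 79.8. That is 40 per arm enrolled and 60 / 2 = 30 per arm completing. The figure reproduces. The concern is procedural and does not depend on it.

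**2. Order of events if Section 12 is followed literally.**
- The allocation is requested (Section 12).
- Consent is given verbally and then documented electronically (Sections 11 and 23). On the phone call, eligibility and discharge home are also confirmed and participation is offered (Section 6).
- The coordinator countersigns and the participant is enrolled (Section 23). Time Point 1 is completed through the texted link or by video call (Section 11).
- The assigned condition is delivered after baseline (Section 11).

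Sections 8 and 11 describe randomising people who are already enrolled. If the reply follows the request promptly, the assignment is known before enrolment. The two descriptions cannot both be the procedure.

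**3. Refused allocations.** Assume that each approach triggers one request; the plan does not say so.
- At the 50% consent rate used for planning in Section 5: 80 / 0.50 = 160 requests, of which 80 (half) meet a refusal.
- At the 40% go/no-go floor in Sections 10 and 12: 80 / 0.40 = 200 requests, of which 120 (60%) meet a refusal.

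If refused slots are discarded, 40/40 is no longer assured. With a balanced list of 160 and 80 consenters unrelated to arm, the number in one arm has variance 80 x 0.5 x 0.5 x (80/159) = 10.1 and SD 3.2, giving a 95% range of about 34 to 46. With simple randomisation the variance is 80 x 0.25 = 20 and the SD 4.5, giving about 31 to 49. If refused slots are instead carried forward, the coordinator knows the arm for the next call with certainty.

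**4. Possible bias in the effect size.** The documents give no figure, so the inputs are assumptions. If a fraction f of one arm is replaced by care partners whose 3-month burden differs by s SD, the unadjusted effect size shifts by f x s.
- Low: 0.10 x 0.5 = 0.05 SD.
- High: 0.30 x 1.0 = 0.30 SD.
- If both arms are steered in opposite directions these double, to 0.10 and 0.60 SD.

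The direction is not known.

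**5. Yardsticks.**
- Standard error of the effect size with 30 per arm: sqrt(2/30) = 0.26, so the 95% half-width is 1.96 x 0.258 = 0.51.
- Detectable difference with 301 per arm, two-sided 5% (assumed): at 80% power, (1.960 + 0.842) x sqrt(2/301) = 0.23; at 90% power, (1.960 + 1.282) x sqrt(2/301) = 0.26. This treats 602 as the number analysed. If 602 were the number enrolled and 25% were lost, 451.5 would be analysed and the 80% figure would be 0.26.
- Effect on sizing the next trial, with n per arm = 2 x (1.960 + 0.842)^2 / d^2: an effect of 0.23 needs 594 in total, 0.28 needs 402 and 0.18 needs 970. A shift of only 0.05 SD either way therefore changes the projected size substantially.

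**The case against.** The strongest reply is that Section 12 fixes when the coordinator asks, not when the data team answers. A reply held until after consent would preserve concealment, and the paragraph's heading and Sections 8 and 11 show that concealment was intended. Consent also has two steps, so the request could fall after verbal agreement and before the e-consent, in which case few refusals would follow a request.

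This stands in part. A reader might infer that allocation is certainly revealed early; the documents do not establish that. But no section says the reply is delayed or coded, and if it is delayed, an early request serves no evident purpose. On the two-step reading the arm could still be known before e-consent, enrolment and baseline. Either way the sentence needs correcting.

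Four stronger inferences are not supported:
- **Most allocations would be wasted.** At the planned 50% it is half. The 60% figure belongs to the go/no-go floor, and both figures assume one request per approach.
- **Discarding refused slots destroys the randomisation.** If refusal is unrelated to arm, the remaining assignments are still random and only the 40/40 split is at risk. Bias needs approach or consent to depend on the arm.
- **Baseline answers are contaminated.** Time Point 1 is self-completed by default, and nothing says the care partner learns the arm first. The risk is greater only where staff assist by video call.
- **The go/no-go decision is biased.** Consent and attrition are judged as pooled rates, no direction or size of bias can be shown for them, and Section 12 states that the effect size is not a go/no-go criterion.

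**Conclusion.** The point holds as a defect in the written procedure. The plan places the allocation request before consent, gives it to the person who decides on entry, and does not say that the answer is held back or how refusals are handled. This conflicts with its own description of blind allocation of enrolled participants.

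What is at risk is the between-arm effect size at 3 months, the primary analysis. Under the assumed steering of 10-30% of one arm by 0.5-1.0 SD, the shift is about 0.05 to 0.30 SD. That is of the same order as the 0.23 SD a 602-participant trial could detect. Most of the range lies below the pilot's own standard error of about 0.26, so random error will usually be the larger source of uncertainty. These figures illustrate scale and do not predict what will happen. The conclusion rests on the order of steps, not on the figures.

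**What to change.** Replace the Section 12 sentence with:

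> The data team will release the next allocation, with a time-stamped log, only after the e-consent is signed and locked and the Time Point 1 survey is submitted; a released allocation is final, and a care partner who declines does not use or reveal an allocation.

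Three consequential edits follow:
- Align Sections 8 and 11 with this order. Section 8 currently treats the 80 enrolled as the 80 randomised.
- State whether 80 is the number consented or the number randomised.
- In Section 12, attrition is counted over consenters. State how those who consent but do not complete Time Point 1, and so are never randomised, enter that denominator.

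The cost is these text changes and a reordered step. Because conditions are already delivered after baseline, the intervention schedule in Section 11 need not move. The downside is that a few consenters may not be randomised, so reaching 80 randomised could take slightly more than 80 consents. The change should be made before recruitment starts or, if it has started, before any further allocation is released.

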13. SPECIMEN BANKING

- *If specimens will be banked for future research, describe where the specimens will be stored, how long they will be stored, how they will be accessed and who will have access to the specimens*
- *List the information that will be stored with each specimen, including how specimens are labeled/coded*
- *Describe the procedures to release the specimens, including: the process to request release, approvals required for release, who can obtain the specimens, and the information to be provided with the specimens.*

N/A

14. DATA MANAGEMENT AND CONFIDENTIALITY

- *Describe the data and specimens to be sent out or received. As applicable, describe:*
 - *What information will be included in that data or associated with the specimens?*
 - *Where and how data and specimens will be stored?*
 - *How long the data will be stored?*
 - *Who will have access to the data?*
 - *Who is responsible for receipt or transmission of data and specimens?*
- *Describe the steps that will be taken to secure the data during storage, use and transmission.*

Regular meetings will take place with the PI and other members of the study team to ensure protocol adherence and data accuracy. This protocol collects data from electronic health records (EHR) and self-reported surveys.

Both EHR and survey data will be collected and stored securely in coded format within REDCap, a Northwell-approved system for collecting and storing research data, including PHI. Only IRB-approved members of the study team will have access to the study REDCap.

Data Variables To-Be Collected:

Care Partner Burden

Post-hospital care partner burden will be assessed using the Zarit Burden Scale (ZBI-22) at 3 months. The ZBI-22 addresses personal strain, which is rated with 5 frequency-related response categories, scored 0 (never) to 4 (nearly always). The total score ranges between 0 and 88 (higher scores indicating higher burden). A score less than 21 has been suggested to indicate care-partner burden. We will measure care-partner burden at baseline, 1 month, and 3 months (long term) using technology. Outcome

measures will be captured through a REDCap link which will be sent to the care partner's smart phone/device.

Care-Related Quality of Life (CarerQol)

Post-Hospital Care-Partner Quality of Life will be measured using the Care-Related Qol-7D. The Care-Related Qol-7D measures well-being (CarerQol-VAS or visual analog scale) and subjective burden (CarerQol-7D). The CarerQol-VAS measures happiness, using endpoints between 'completely unhappy' (0) and 'completely happy' (10). Subjective burden is measured on 7 dimensions (fulfillment, relational problems, mental health, daily activities problems, physical health, and support), and rated as (i) no, (ii) some, and (iii) a lot. The weighted score ranges from 0-100 (worst to best caregiving situation). We will measure care-partner quality of life using technology. Outcome measures will be captured through a REDCap link which will be sent to the care partner's smart phone/device.

The Caregiver Analysis of Reported Experiences with Swallowing Disorders (CARES)

(CARES) is a 26-item survey (scored as "yes" or "no") divided across 2 subscales: Part A-Checklist of Behavioral Changes (10 items) and Part B-Measures of Subjective Caregiver Stress (16 items). Each part is scored separately (1 point for every "yes" response) out of 10 (Part A) and 16 points (Part B). Part A is scored with a maximum of 10 points and Part B is scored with a maximum of 16 points. Scores are continuous, with lower scores indicating more self-efficacy with behavioral (Part A) and stress (Part B) management. CARES Parts A and B will be administered at baseline, 1 month, and 3 months using technology. Outcome measures will be captured through a REDCap link which will be sent to the care partner's smart phone/device.

The Edinburgh Feeding Evaluation in Dementia Questionnaire (EdFED-Q)

The Edinburgh Feeding Evaluation in Dementia Questionnaire (EdFED-Q) is an 11-item instrument, which assesses eating and feeding problems in people with late-stage dementia (less than 5 minutes to complete). The care partner assigns a score (0 to 2, never, sometimes, or often occurring) to each item; higher scores (range 0 to 20) indicate greater feeding dysfunction. The EdFED-Q will be administered at baseline, 1 month and 3 months using technology. Outcome measures will be captured through a REDCap link which will be sent to the care partner's smart phone/device.

Quality of Life in Late-Stage Dementia Scale (QUALID)

The Quality of Life in Late-Stage Dementia Scale (QUALID), an 11-item, is a reliable and valid scale, administered to care partners for rating QoL in late-stage dementia. A 5-point scale is used to capture the frequency of each item (scores range from 11 to 55, low scores reflect a higher QoL). The QUALID will be administered at 1 month and 3 months using technology.

Outcome measures will be captured through a REDCap link which will be sent to the care partner's smart phone/device.

Sociodemographics

The sociodemographic questions will consist of patient's and care partner's age, gender, race or ethnicity, income, and education.

Clinical Data

Clinical data will consist of patient diagnoses (clinical and psychiatric comorbidities); patient's level of cognitive impairment (Clinical Dementia Rating Scale, CDRS), and patient's OD severity (recommendation of dysphagia diet types or non-dysphagia diet types).

Caregiving Measures

Caregiving measures will consist of the relationship between care partner and patient; time since assuming the care partner role; number of other care partners; overall number of caregiving responsibilities (e.g., financial, physical, medical); OD-related caregiving responsibilities (e.g., purchasing and preparing food, feeding); and other factors of caregiver burden such as clinical and psychiatric comorbidities.

Patient-Centered Outcomes

Patients will be assessed for outcomes including 1) acute care visits (emergency department visits and hospital readmissions; differentiating between aspiration and non-aspiration related complaints); 2) dehydration (requiring intravenous or subcutaneous fluid administration); 3) nutritional intake (weight loss greater than 3 kg, 1-3 kg, and no weight loss; derived from the Mini Nutritional Assessment, MNA); 4) behavioral and psychological symptoms of dementia (BPSD, Neuropsychiatric Inventory Questionnaire, NPI-Q).

National Institutes on Aging Clinical Research Operations & Management System (CROMS) Screening and Enrollment Questionnaires

The funding agency of this study requires the collection of standardized demographic information from all funded clinical trial aims and enrollment to facilitate early interventions to help with enrollment challenges, particularly among underrepresented populations. Participants will have the ability to select "prefer not to answer" to any of the items listed. Variables collected include age, sex, gender, sexual orientation, race, ethnicity, patient's cognitive status, education level, household income, occupation category, marital status, living situation, primary language spoken, insurance status, zip code, and dates associated with screening, enrollment, and study participation

All data collected for this research will be maintained in its original and unaltered source data state indefinitely and stored within the Quantitative Intelligence Data

Lake, on a Microsoft Azure platform, which complies with all Northwell security standards and best practices for processing Protected Health Information (PHI). QI, as Honest Brokers, will have access to direct identifiers for linkage purposes and will retain the map/linkage between datasets in the event that data needs to be re-identified and/or for traceability purposes. Data collected for this study may be used for future research in coded format without additional consent pursuant to any conditions outlined within the consent form participants signed, and with appropriate IRB approval as required. Access to identifiable data is controlled and limited to IRB-approved individuals who have completed all required human subjects protection training.

This research is funded by the NIH; a Certificate of Confidentiality has been issued for this research. Certificates of Confidentiality (CoCs) protect the privacy of research subjects by prohibiting disclosure of identifiable, sensitive research information to anyone not connected to the research except when the subject consents or in a few other specific situations. In addition, per NIH requirement for Data Management and Sharing, scientific data generated as a result of this research will be shared broadly via OpenScience: <https://cos.io/>. The Open Science Framework is a free, open-source web application built to provide researchers with a free platform for data and materials sharing. There will be no identifiable data posted to this website. In addition, a description of this clinical trial will be available on <http://www.ClinicalTrials.gov>, as required by U.S. Law. |

